6.2 Subject Inclusion Criteria

In order to participate in this study, a patient must meet all of the following criteria:

- Age 18 years or older
- Capable of providing written and oral informed consent in English

Meets criteria for unresectable disease:

- Locally advanced disease based on preoperative work-up demonstrating that the tumor is unresectable due to portal vein, hepatic artery, and/or bile duct involvement, insufficient hypertrophy response of the future liver remnant after portal vein embolization, or patients not able to tolerate major liver surgery
- Found to be unresectable intraoperatively based on vascular, biliary, or lymph node (N2) involvement upon exploratory laparotomy
- Patients will be assessed for chemotherapy prior to treatment with RE, but given the common problem of recurrent cholangitis, some patients will not be candidates for chemotherapy until after RE is performed.

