Patients with advanced PHC generally receive optimal palliative chemotherapy and adequate biliary drainage with metal stenting. In the current study, patients undergo local ablative therapy of the tumor. As it may be difficult to distinguish local RE-related effects on computed tomography scans or MRI from residual tumor tissue or tumor progression, it was decided that all patients in the current study will be proposed to receive palliative chemotherapy.

Palliative chemotherapy

All patients will be seen by the medical oncologist at MSKCC prior to intraoperative RE is performed, and palliative chemotherapy will be discussed. Patients will be offered optimal palliative chemotherapy according to medical oncology preferences. Palliative chemotherapy is not mandatory to participate in the trial, as some patients will not be eligible due to ongoing

cholangitis. Palliative chemotherapy post procedure is preferably started within 6 weeks after IRE when the patient has recovered from definitive metal biliary stent placement. The start of chemotherapy may be postponed in the event of IRE- or biliary drainage-related complications. However, delay of start to chemotherapy is not expected. In fact, we suspect that patients will be likely have a better chance of being treated with chemotherapy and for a longer duration of time, due to stent patency.

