14.1 BIOSTATISTICS

The primary objective of this study is to assess biliary drainage patency after IRE treatment of hilar cholangiocarcinoma. In patients with plastic percutaneous drains this is defined as ability to remove plastic biliary drains within 15 months of the IRE procedure without need for reinsertion of a drain or stent. For patients with metal stents in place the definition of patent biliary drainage is 4-months without cholangitis post IRE procedure.

We will enroll 20 patients. Mean patency is approximately 1.5 months for plastic stents and 4 months for metal stents. Assuming an exponential distribution time to failure, we extrapolate that the patency rate at 15 months for plastic stents and at 4 months for metal stents will approximately be 37% and we will use this number as our historical control rate. If 10 or more of the 20 patients we plan to enroll display patency (at 1.5 months for plastic and 4 months for metal stents) then we will recommend IRE for further study. This decision rule has 8% Type I error and 12% Type II error for distinguishing between patency rates of 37% and 65%.

The secondary outcomes of interest are:

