- Safety will be assessed by determining the proportion of patients experiencing a clinically relevant complication within 30 days post-IRE, defined as CTCAE (version 5.0) grade 3 or higher complications requiring re-intervention, prolonged hospital stay, intensive care admission, re-admission or leading to mortality. After accruing the first 8 patients, we will do an interim analysis of safety. If 4 or more of these 8 patients experience a grade 3 complication within 30 days post-IRE (as defined above) then the study will stop for lack of safety. A 30 day observation window will follow after the eighth patient is enrolled. If one patient in the first 8 patients has a grade 4 or 5 complication the study will be halted. If none of these conditions are met then we will accrue another 12 patients. If 6 or fewer of the total group of 20 patients have a grade 3 complication we will conclude that the safety endpoint has been met. This safety monitoring rule has an 81% chance of stopping the study early for safety concerns if the true probability of complications is 35%. If there is a death during the 30-day post-procedure period the study will be halted to examine the relationship of death to the procedure. We will examine the cause of death for all 30-day deaths and determine if it could be related to the procedure. If the death can possibly be related to the

procedure then the protocol will be stopped. To continue with the protocol after a death, we will submit to RB all the documentation related to the ascertainment of cause of death and describe how it cannot be related to the RE procedure.

- Duration of hospital stay will be summarized with median, range and quartiles.
- Quality of life will be summarized by average subscale scores at each visit and change from previous visit will also be reported by the same summary statistics.
- Tumor response on CT imaging and blood biomarker response will be reported as a binomial proportion with a 95% confidence interval. RECIST criteria cannot be applied to Klatskin tumors as they are radiographically difficult to assess. This instead will be a subjective evaluation of the ablation zone to determine the appearance of an RE associated ablation zone in the hilar area. This is currently unknown.
- Time between RE and start of palliative chemotherapy will be summarized with median, range and quartiles
- Duration of palliative chemotherapy will be summarized using Kaplan-Meier statistics

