- Progression-free and overall survival will be summarized using Kaplan-Meier statistics
- Success rate of completing RE reported as a binomial proportion with a 95% confidence interval

Expected accrual rate, accrual duration, and study duration

Our anticipated accrual rate is approximately 1 patient per month. This accrual rate is based on analysis of potentially eligible patients seen at our Outpatient Clinic in the last 2 years (2016 and 2017). Thus, it should take approximately 1.5 years to accrue the 20 patients needed for the trial. Allowing for 2 months of follow-up to obtain the primary endpoint on the last patient enrolled and 4 months to assemble, analyze and interpret the data the total study duration is projected to be at most 2 years. Patients who consent to the procedure but do not have it will be considered a screen failure. They will be replaced by another patient and their questionnaire data will be removed from the study.

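### The planned median time from IRE to chemotherapy has no denominator and no rule for patients who never start, so in practice it will describe starters only

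*Combined protocol and SAP*

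**What the plan says.** Section 2.1 lists the time from IRE to palliative chemotherapy as a secondary outcome. The whole analysis is one line in Section 14.1: "Time between RE and start of palliative chemotherapy will be summarized with median, range and quartiles". The next two items there use a time-to-event method: "Duration of palliative chemotherapy will be summarized using Kaplan-Meier statistics" and "Progression-free and overall survival will be summarized using Kaplan-Meier statistics". The sample is small and single-arm: "We will enroll 20 patients".

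Four other statements bear on who will have a start date:

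- Section 9.0, on patients who may never start: "Palliative chemotherapy is not mandatory to participate in the trial, as some patients will not be eligible due to ongoing" cholangitis.
- Section 6.2, on candidacy before the procedure: "some patients will not be candidates for chemotherapy until after RE is performed".
- Section 9.0, on timing: "Palliative chemotherapy post procedure is preferably started within 6 weeks after IRE", subject to recovery from metal stent placement.
- Section 9.0, on delay: "The start of chemotherapy may be postponed in the event of IRE- or biliary drainage-related complications".

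Section 9.0 adds that no delay is expected, and that IRE should make it likelier that patients get chemotherapy and stay on it longer. The proportion who start is not an outcome in Section 2.1 or Section 14.1. The withdrawal rules in Section 13.0 cover patency and complications only.

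**The concern.** A patient who never starts chemotherapy has no time from IRE to chemotherapy. The plan does not say whether such a patient is left out, ranked last or censored. A range cannot be computed with a missing time, so the natural reading by whoever programs the table is to use starters only.

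Two things are then lost. First, the summary is silent on how many of the treated patients reach chemotherapy, which is the quantity that Section 9.0 expects IRE to improve. Second, a starters-only median does not worsen when patients fail to start. It can stay level, or even shorten, if those who would have started late are the ones who drop out. A reader could take a short median as a sign that chemotherapy was not held up, when many patients never received it.

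**Working it through.** **Stated figure.** There is none to reproduce. The documents give no start rate, target or precision for this outcome. Both illustrations below rest on assumed inputs.

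**Illustration 1: evenly spread starts.** Inputs: N = 20 (Section 14.1); s starters, varied from 20 to 8 (assumed); start times spread evenly over 3 to 9 weeks (assumed). The i-th start is at

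t(i) = 3 + 6(i − 1)/(s − 1) weeks.

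The median is taken as the earliest time by which at least half the group has started. Among starters that is the start numbered s/2, rounded up. Among all 20 it is the 10th start, with non-starters never reaching the event. For s = 12:

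- Starter median, 6th start: 3 + 6 × 5/11 = 5.7 weeks.
- All-patient median, 10th start: 3 + 6 × 9/11 = 7.9 weeks.
- Started by 6 weeks: 6 of 20 = 30%.

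| Starters of 20 | Starter median (weeks) | All-patient median (weeks) | All patients started by 6 weeks |
|---|---|---|---|
| 20 | 5.8 | 5.8 | 50% |
| 18 | 5.8 | 6.2 | 45% |
| 16 | 5.8 | 6.6 | 40% |
| 14 | 5.8 | 7.2 | 35% |
| 12 | 5.7 | 7.9 | 30% |
| 11 | 6.0 | 8.4 | 30% |
| 10 | 5.7 | 9.0 | 25% |
| 8 | 5.6 | not reached | 20% |

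The small movements in the second column come from the median convention. The times are symmetric about 6 weeks, so averaging the two middle values would give 6.0 in every row. The starter median therefore carries no information about the number who start. The all-patient upper quartile is the 15th start, so it is not reached with 14 or fewer starters.

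**Illustration 2: competing constant hazards.** Let a be the hazard of starting and b the hazard of an event that rules out starting. Fix a = ln 2/6, a 6-week median when b = 0 (assumed). Then

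- P(start) = a/(a + b)
- starter median = ln 2/(a + b)
- all-patient median = −ln(1 − 0.5/P(start))/(a + b), reached only if P(start) exceeds 50%.

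| b/a | P(start) | Starter median (weeks) | All-patient median (weeks) |
|---|---|---|---|
| 0 | 100% | 6.0 | 6.0 |
| 0.25 | 80% | 4.8 | 6.8 |
| 0.5 | 67% | 4.0 | 8.0 |
| 1 | 50% | 3.0 | not reached |

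For b/a = 0.5, the starter median is 6/1.5 = 4.0 weeks. The all-patient median is −ln(1 − 0.75)/(1.5 × ln 2/6) = 2 ln 2/(0.25 ln 2) = 8.0 weeks. Here the planned statistic improves while access to chemotherapy gets worse.

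**Precision at n = 20.** For 6 of 20 started by 6 weeks, the standard error is √(0.30 × 0.70/20) = 0.102. A rough 95% interval is 30% ± 1.96 × 10.2 points, or about 10% to 50%.

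**The case against.** The case for leaving the plan alone has several parts.

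- *The text is silent, not wrong.* A reader might infer that the plan restricts the summary to starters, or that no median could cover everyone. Neither follows. Section 14.1 sets no restriction, and a median over all 20 with non-starters ranked last exists if at least half start. What stands is that the plan does not choose this, and that the range, and the upper quartile with enough non-starters, would still fail.
- *The plan foresees fewer kinds of non-starter than one might suppose.* A reader might infer that it expects patients never to start because of complications, refusal or death. Section 9.0 names only ongoing cholangitis as a reason for ineligibility; complications may postpone the start, and refusal and death are not given as reasons. Section 6.2 describes candidacy that comes later, and Section 9.0 says that chemotherapy will be proposed to everyone. Some non-starters are therefore foreseen, but not how many.
- *No claim is being tested.* The expectations about delay and access in Section 9.0 have no comparator, threshold or hypothesis, so it would be too strong to say that a formal conclusion rests on this median. It remains true that nothing planned describes access to chemotherapy.
- *The Kaplan-Meier contrast proves little.* Duration of chemotherapy exists only in starters, and Kaplan-Meier there handles patients still on treatment. Its use next door does not make the plan inconsistent.
- *A simple count would do.* Giving the number who started beside the median would remove most of the risk of misreading. That is fair. The cumulative incidence adds timing in all treated patients and handles anyone without a start date at data cut-off.

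**Conclusion.** The point holds as a gap in specification. Time from IRE to chemotherapy has no denominator and no rule for non-starters, in a plan that foresees some. As written it will in practice give a starters-only summary, which cannot show how many treated patients reach chemotherapy and can look prompt when few do.

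The size is unknown because the start rate is unknown. With no non-starters there is no distortion. Under the assumed 3-to-9-week spread, the gap between the two medians is 0.8 weeks with 16 starters (6.6 − 5.8) and 2.2 weeks with 12 (7.9 − 5.7); with 8 starters the all-patient median is not reached. Other assumed spreads would give other gaps. The existence of the gap in the plan does not depend on them.

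The change is worth making, but its weight is modest: the outcome is secondary and descriptive, and nothing here touches the primary decision rule.

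**What to change.** In Section 14.1, define the analysis set for this outcome as all patients treated with IRE, and the event as the first palliative chemotherapy after IRE. Then report:

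1. The number and proportion who start chemotherapy after IRE.
2. The cumulative incidence of starting from the IRE date, with death before chemotherapy as a competing event and censoring at last contact. Give the estimate at 6 weeks, the plan's stated preference, with a 95% CI. Plain Kaplan-Meier that censors deaths would overstate the chance of starting.
3. Separately, how many patients had chemotherapy before IRE. Section 6.2 has patients assessed for it beforehand, so some may have received it.
4. The planned median, range and quartiles, kept as a supplement and labelled as conditional on starting, with the number of starters shown.

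The cost is one small extra analysis. The IRE, chemotherapy-start and death dates are already implied by the listed outcomes. Section 10.0 does not name the chemotherapy start date among the data to be collected, so it should be added explicitly. The estimates will be imprecise with 20 patients and should be presented as descriptive.

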The primary outcome is patency of biliary drainage. In patients with plastic percutaneous drains this is defined as ability to remove plastic biliary drains within 1.5 months of the IRE procedure without need for reinsertion of a drain or stent. For patients with metal stents in place the definition of patent biliary drainage is 4-months without cholangitis post IRE procedure.

Secondary outcomes are the success rate of completing IRE (defined as percentage of planned pulses completed}, complications, duration of hospital stay, quality of life, impact of IRE on post-procedural CT imaging and blood biomarker response, time between IRE and start of palliative chemotherapy, metal stent patency, progression-free and overall survival. Prolonged hospital stay is defined as hospital stay for more than 10 days. The average length of stay for major liver procedures is 8 days. Patients with hilar cholangiocarcinomas often have biliary drains and stents so require extra care as inpatients after any procedure. Complications will be defined as patients experiencing a clinically relevant IRE-related complication within 30 days post-IRE, defined as CTCAE (version 5.0} grade

3 or higher complications requiring re-intervention, prolonged hospital stay, intensive care admission, re-admission or leading to mortality.

Follow up: 30 days after intervention for the primary endpoint. For survival endpoints, there is a 2-year followup.

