2.1 OBJECTIVES AND SCIENTIFIC AIMS

Primary objective:

The primary objective of this study is to assess patency of biliary drainage. In patients with plastic percutaneous drains this is defined as ability to remove plastic biliary drains within 1.5 months of the IRE procedure without need for reinsertion of a drain or stent. For patients with metal stents in place the definition of patent biliary drainage is 4-months without cholangitis post IRE procedure.

Secondary objective:

The secondary outcomes of interest are

- Duration of hospital stay
- Complications
- Quality of life
- Tumor response on CT imaging and blood biomarker response
- Time between IRE and start of palliative chemotherapy
- Duration of palliative chemotherapy
- Progression-free and overall survival
- Success rate of completing IRE (defined as percentage of planned pulses completed)

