13.0 CRITERIA FOR REMOVAL FROM STUDY

Subjects can leave the study at any time for any reason if they wish to do so without any consequences. The investigator can decide to withdraw a subject from the study for urgent medical reasons. Patients who withdraw before 120 days due to complications will be counted as failures for the patency objective. Patients who withdraw before 30 days will be counted as having experienced a complication for the purposes of the secondary objective.

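### Follow-up for the primary endpoint is given as 30 days and as 2 months, but metal-stent patency is read at 4 months; the projected 2-year total rests on the 2-month figure

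*Combined protocol and SAP*

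**What the plan says.** **Endpoint.** Section 2.1 states: "For patients with metal stents in place the definition of patent biliary drainage is 4-months without cholangitis post IRE procedure". For plastic drains the window is 1.5 months. The decision rule in Section 14.1 uses the same times, counting patients who "display patency (at 1.5 months for plastic and 4 months for metal stents) then we will recommend IRE for further study". Section 12.0 also uses 4 months for metal-stent failure, and Section 13.0 uses 120 days: "Patients who withdraw before 120 days due to complications will be counted as failures for the patency objective".

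**Length of follow-up for that endpoint.** Two places state it, and they differ.
- Section 1.0: "Follow up: 30 days after intervention for the primary endpoint. For survival endpoints, there is a 2-year followup".
- Section 14.1, in the paragraph on accrual and duration: "Allowing for 2 months of follow-up to obtain the primary endpoint on the last patient enrolled".

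**Timeline.** The same paragraph of Section 14.1 says "Our anticipated accrual rate is approximately 1 patient per month", that "it should take approximately 1.5 years to accrue the 20 patients needed for the trial", allows 4 months for analysis, and concludes that "the total study duration is projected to be at most 2 years".

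**Visits.** Section 10.0 lists clinic visits at 2 and 4 weeks and then at about 6, 12 and 24 months. Quality of life is collected at 3, 6, 9, 12 and 24 months, within 1 month either way.

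**The concern.** The plan gives three different times at which the primary endpoint is complete for a patient: 30 days, 2 months, and up to 4 months. Only the last agrees with the endpoint definition. The clinic schedule does not settle the matter, because it passes from 4 weeks to about 6 months and names no 4-month visit.

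Two things are at stake. First, the two sentences that say how long primary-endpoint follow-up lasts are both too short, and no sentence says that the primary analysis waits for the last patient's 4-month date. If either short figure were used as the cutoff, the latest metal-stent patients would be analysed with their windows still open. The plan does not say how to count them, since Section 13.0 covers only withdrawals due to complications. In a trial of 20 patients judged against a fixed count of 10, a few such patients can matter. Second, the stated total duration is too short for the primary analysis as defined, and it cannot contain the 2-year follow-up of patients enrolled later.

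**Working it through.** **Inputs**

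| Quantity | Value | Source |
|---|---|---|
| Sample size | 20 | Section 14.1 |
| Accrual rate | about 1 per month | Section 14.1 |
| Accrual duration | about 1.5 years = 18 months | Section 14.1 |
| Last-patient follow-up, primary endpoint | 2 months | Section 14.1 |
| Primary-endpoint follow-up | 30 days | Section 1.0 |
| Endpoint window | 1.5 months plastic, 4 months metal | Sections 1.0, 2.1, 14.1 |
| Analysis time | 4 months | Section 14.1 |
| Stated total | at most 2 years = 24 months | Section 14.1 |
| Survival and last quality-of-life time | 2 years, 24 months | Sections 1.0, 10.0 |

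Section 14.1 twice prints 15 months for plastic drains. I read this as 1.5 months with the decimal point lost in the text, and nothing below depends on it.

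**Step 1: the plan's own total.** Accrual + last-patient follow-up + analysis = 18 + 2 + 4 = 24 months. The figure reproduces exactly, with no slack.

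**Step 2: the same sum with the defined window.**
- Stated accrual duration: 18 + 4 + 4 = 26 months.
- Stated accrual rate taken literally (20 patients at 1 per month = 20 months): 20 + 4 + 4 = 28 months.
- The two accrual figures differ slightly, since 20/18 = 1.1 per month. Both are given as approximate.

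**Step 3: what holding to 24 months would mean.** On 18 months of accrual the last 4-month date is 18 + 4 = month 22. That leaves 24 − 22 = 2 of the planned 4 months for analysis.

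**Step 4: patients short of follow-up if a stated figure were the cutoff.** Enrolment is taken as the date of IRE, and 30 days as 1 month.

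| Entry pattern | Cutoff after last entry | Follow-up of the last patients (months) | Under 4 months | Under 1.5 months |
|---|---|---|---|---|
| Months 1 to 20, one each | 2 months | 4, 3, 2 | 2 | 0 |
| Months 1 to 20, one each | 1 month | 4, 3, 2, 1 | 3 | 1 |
| 20 spread evenly over months 0 to 18 | 2 months | 4.8, 3.9, 2.9, 2.0 | 3 | 0 |
| 20 spread evenly over months 0 to 18 | 1 month | 4.8, 3.8, 2.9, 1.9, 1.0 | 4 | 1 |

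A 2-month cutoff therefore leaves the last 2 to 3 patients short of 4 months. A 30-day cutoff leaves the last 3 to 4 short, and the last patient also misses the 1.5-month plastic-drain window. Being short of 4 months matters only for patients with metal stents.

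**Step 5: long-term follow-up.** The last patient's 24-month date is 18 + 24 = month 42, or 20 + 24 = month 44, before any analysis time.

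**The case against.** The strongest reply is that the duration paragraph is a projection made from approximate figures. It is not an analysis rule, and its sum is correct for the inputs it uses. No section sets a data cutoff at 30 days or 2 months. The decision rule counts metal-stent patency at 4 months, so such a patient cannot properly be called a success earlier, and the 120-day withdrawal rule agrees. Section 12.0 treats stent occlusion as a clinical event and asks patients to report symptoms at once, so the lack of a 4-month visit does not prevent ascertainment. The last 4-month date, month 22, falls inside the printed 24 months. The 2-year survival follow-up is stated separately in Section 1.0, so the total may be meant only for the primary analysis.

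Much of this stands, and it limits the point. The harm to the result is conditional, the number of metal-stent patients is not given, and the missing visit shows only that the schedule does not resolve the conflict. The reply does not remove the conflict itself. Approximate accrual cannot reconcile 2 months, still less 30 days, with a 4-month endpoint. Two months would suffice only if the last patients enrolled all had plastic drains, which the plan does not say. The decision rule implies waiting for the 4-month date, but the only sentences about length of follow-up point the other way.

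**Conclusion.** The concern holds. Both stated follow-up periods for the primary endpoint are too short for the endpoint as defined: 30 days for either drain type, 2 months for metal stents. The stated total of at most 24 months should be about 26 months to the primary analysis, or about 28 at exactly one patient per month. The survival and quality-of-life follow-up ends at about month 42 to 44. At most 3 patients (2-month cutoff) or 4 patients (30-day cutoff) would lack a 4-month window, and only if such a cutoff were applied and they had metal stents.

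These figures assume that IRE takes place at enrolment and that accrual does not pause during the 30-day observation window after the eighth patient. A one-month pause added to the accrual period would make the range 27 to 29 months. The endpoint, sample size and decision rule are unaffected by this point. It should be corrected because the stated follow-up, if followed, could not yield the primary endpoint for every patient.

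**What to change.** - **Section 14.1, duration paragraph:** change the last-patient follow-up from 2 to 4 months.
- **Section 1.0, follow-up line:** replace 30 days for the primary endpoint with 1.5 months (plastic drains) and 4 months (metal stents), and keep 30 days for complications.
- **Section 14.1, analysis timing:** state that the primary analysis is not done before the last patient's primary-endpoint window, up to 4 months, has closed.
- **Section 14.1, total:** restate the duration as about 26 to 28 months to the primary analysis, recomputed if accrual is to pause after the eighth patient. Give a separate date for the 24-month survival and quality-of-life results, about month 42 to 44 plus analysis time.

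Section 18.1 requires the consent form to give the study length and likely follow-up, so its wording should be checked against the corrected figures. The cost is wording and a longer stated duration, with no extra patients, visits or tests.

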10.0 EVALUATION DURING TREATMENT/INTERVENTION

Data collection prior and during hospital admission

Prior to the procedure we will collect:

Baseline parameters: Demographics, tumor characteristics and serum markers that will be routinely collected are: age, sex, comorbidity, body mass index (BMI), tumor size, tumor growth pattern, arterial or venous vascular involvement, nodal status, cancer antigen (CA) 19.9, IgG4, albumin, C-reactive protein (CRP), leukocytes. If IgG4 level is normal at baseline further measurements are not necessary and will therefore not been included in the follow up.

During the hospital stay, we will collect data on serum liver enzymes and inflammatory parameters (WBC, CRP).

Follow up

During follow up, after discharge, patients will be seen in the outpatient clinic, as is routine practice for post-operative/post-procedural patients, for clinical evaluation and laboratory testing of liver enzymes, inflammatory parameters (WBC, CRP), Albumin and tumor markers (CA 19.9).

In this study, patients will also be seen in the outpatient clinic at 2 weeks, 4 weeks, and approximately 6, 12, and 24 months, as is routinely performed for clinical follow-up currently. Laboratory tests obtained at visits after the first post-procedure visit will be determined by the surgeon.

The date of disease progression is defined as the date of CT scan on which the first suspected lesion is defined.

Quality of life will be assessed at the initial clinic visit, initial post-operative visit (2 weeks from surgery), and at subsequent post-operative visits \pm 1 month from 3, 6, 9, 12, and 24 months following the IRE procedure. The Functional Assessment of Cancer Therapy-Hepatobiliary instrument (FACT-Hep) will be used. If patients are unable to complete the questionnaires at the designated visits for any reason, they will be offered the option of returning the QOL via mail.

Imaging

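### The projected total duration of at most 2 years contradicts the 2-year survival follow-up and the 24-month clinic and quality-of-life visits, and no later data cutoff or analysis is stated

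*Combined protocol and SAP*

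**What the plan says.** The timeline is in Section 14.1, under expected accrual and study duration. It has three components:

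- Accrual: "Our anticipated accrual rate is approximately 1 patient per month", from which "it should take approximately 1.5 years to accrue the 20 patients needed for the trial".
- Follow-up of the last patient: "Allowing for 2 months of follow-up to obtain the primary endpoint on the last patient enrolled".
- Data handling: "4 months to assemble, analyze and interpret the data".

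From these it concludes that "the total study duration is projected to be at most 2 years". The sample size, earlier in the same section, is "We will enroll 20 patients".

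Two other places set a longer horizon. The follow-up paragraph of Section 1.0 says "For survival endpoints, there is a 2-year followup". Section 10.0 schedules FACT-Hep, with a window of one month either side, at "3, 6, 9, 12, and 24 months following the IRE procedure", and it also lists a clinic visit at about 24 months.

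Section 14.1 plans Kaplan-Meier summaries of overall and progression-free survival, and average quality-of-life subscale scores at every visit. It gives no data cutoff for them, and no analysis later than the one inside the 2-year total.

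**The concern.** Patients enter over about a year and a half and the last 4 months are set aside for data handling, so a 24-month study cannot give each patient 24 months of observation. The planned follow-up and the stated duration cannot both be carried out.

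If the study were closed and analysed on the Section 14.1 timeline, the 24-month quality-of-life assessment would have no data. The survival curves would rest mostly on patients with about a year or less of potential follow-up. Section 3.0 cites survival of 14 to 16 months for this population, so many observations would be censored before that point. Section 18.1 also requires the consent form to state how long the study lasts and what follow-up is likely, so the two durations bear on what patients are told.

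**Working it through.** **Inputs.** From Section 14.1: 20 patients, about 1 per month, accrual about 18 months, 2 months on the last patient, 4 months of analysis, total at most 24 months. From Sections 1.0 and 10.0: 24 months of follow-up, with the last FACT-Hep window opening at 24 − 1 = 23 months. From Section 3.0: survival of 14 to 16 months in this population, and a median progression-free survival of 8 months on chemotherapy.

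**Step 1: reproduce the stated total.** 18 + 2 + 4 = 24 months, which matches. At the stated rate, however, 20 patients ÷ 1 per month = 20 months, and the sum becomes 20 + 2 + 4 = 26 months. An 18-month accrual needs 20 ÷ 18 = 1.1 patients per month.

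**Step 2: potential follow-up per patient.** Follow-up = data cutoff − entry time, with 20 evenly spaced entries over an accrual period of A months. The first patient enters either at month 0 (entries 0 to A) or after one interval (entries A/20 to A). Each cell gives both versions in that order.

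| Accrual, data cutoff | Shortest | Longest | Median | ≥12 months | ≥23 months | ≥24 months |
|---|---|---|---|---|---|---|
| 18, month 20 (as stated) | 2 / 2 | 20 / 19.1 | 11.0 / 10.6 | 9 / 8 | 0 / 0 | 0 / 0 |
| 20, month 22 | 2 / 2 | 22 / 21 | 12.0 / 11.5 | 10 / 10 | 0 / 0 | 0 / 0 |
| 18, month 24 (no analysis time) | 6 / 6 | 24 / 23.1 | 15.0 / 14.6 | 13 / 13 | 2 / 1 | 1 / 0 |
| 20, month 24 (no analysis time) | 4 / 4 | 24 / 23 | 14.0 / 13.5 | 12 / 12 | 1 / 1 | 1 / 0 |

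With the 4 analysis months kept, as Section 14.1 keeps them, no patient reaches 23 or 24 months under either accrual figure. If data were collected to the last day of month 24, at most 1 patient would reach 24 months and at most 2 the quality-of-life window.

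**Step 3: expected deaths.** Section 3.0 does not call its 14 to 16 months a median. Treating it as one, with exponential survival, is an assumption. Expected deaths = Σ(1 − 2^(−fᵢ/m)), where fᵢ is patient i's potential follow-up and m the median.

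- Stated timeline (18, month 20): 8.0 / 7.7 for m = 14 and 7.2 / 7.0 for m = 16.
- Entries at months 1 to 20, cutoff month 22: 8.2 for m = 14 and 7.5 for m = 16.
- 24 months for all: 20 × (1 − 2^(−24/14)) = 13.9 and 20 × (1 − 2^(−24/16)) = 12.9.

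On the stated timeline, 7.7 to 8.0 of 13.9 deaths, or 7.0 to 7.2 of 12.9, would be observed, which is roughly 55% of them.

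**Step 4: progression-free survival.** With m = 8, also exponential, the stated timeline gives 11.4 / 11.2 expected events, against 20 × (1 − 2^(−24/8)) = 17.5 with full follow-up. That is roughly 65%, a smaller relative loss.

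**Step 5: time needed for the promised follow-up.** 18 + 24 + 4 = 46 months, or 20 + 24 + 4 = 48 months. Allowing for the extra month of the quality-of-life window gives 47 to 49.

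**Step 6: the primary endpoint inside the same sum.** Two months on the last patient covers the 1.5-month plastic-drain window but not the 4-month metal-stent window. With 4 months the sum is 18 + 4 + 4 = 26, or 20 + 4 + 4 = 28.

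**The case against.** The strongest reply is that the 2-year figure is a mislabelled time to the primary analysis. Its follow-up component is explicitly for the primary endpoint, and Section 1.0 gives the primary and survival follow-up separately. Nothing in the documents says that follow-up stops at year 2 or that the 24-month visit is dropped. This is a plausible account of what was intended, and a reader should not infer that the sponsor has decided to stop early. But Section 14.1 calls the figure the total, and no section states that follow-up continues or that a later analysis is planned. The text needs correcting on either reading.

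A second reply concerns the consequences. A reader might infer that overall survival could not be examined at all. The documents do not support that. Under the same exponential assumptions, the Kaplan-Meier median for overall survival is still reached in roughly 55% to 75% of simulated trials at the early cutoff, against about 94% to 98% with full follow-up. For progression-free survival with an 8-month median it is reached in about 97%. The trial is also single-arm with no survival threshold, so even full follow-up would not formally test the hope in Section 12.0 of longer survival. This reply stands: the loss is precision and all 24-month data.

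A third reply is that both the accrual rate and the accrual duration are stated as approximate, so the gap between 18 and 20 months is small. That is fair. The main contradiction does not depend on it.

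**Conclusion.** The contradiction is real and follows from the protocol's own figures. Followed as written, 0 of 20 patients reach 24 months or the 23-month opening of the last quality-of-life window, whether accrual takes 18 or 20 months. This holds as long as the 4 analysis months are kept. It would be too strong to say that no patient could reach 24 months under any reading, since 1 could, and 2 could enter the window, if data were collected to the last day of month 24.

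The size of the loss is about 7 to 8 observed deaths instead of 13 to 14, assuming evenly spaced entry and exponential survival with a median of 14 to 16 months. The effect on progression-free survival is smaller. A reader might also infer that the trial's main conclusion is at risk. It is not, on this ground: the patency decision rule and the 30-day safety rules do not use 24-month data, and the outcomes affected are secondary and descriptive.

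The 2-year total is also too short on its own terms: 26 months at the stated accrual rate, and 26 to 28 months if the last patient has a metal stent.

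**What to change.** Restate the timeline in Section 14.1 with two milestones.

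1. Relabel the 2-year figure as the projected time to the patency and safety analysis. Correct its sum so that the accrual duration agrees with the accrual rate and the follow-up covers the last patient's full patency window.
2. Add a final analysis of overall survival, progression-free survival and quality of life 24 months after the last IRE, and give the total study duration as about 46 to 48 months (18 to 20 accrual + 24 follow-up + 4 analysis).

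State that survival results reported at the first milestone are interim, and check that the consent form gives the same durations.

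The cost is that the protocol stays open about two years longer and FACT-Hep collection continues. FACT-Hep is a study addition to the standard work-up (Section 8.0), so that part is not free. Section 10.0 describes the clinic visits and scans as routine care, so no new procedures are needed.
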